## 6.1.1. Screening Period Stage 1 (Initial Screening Visit)

- Informed consent.
- Demographics and general medical history.
  - Assessment of depression by medical history (Use of PHQ-9 is optional and suggested as a tool to assess seriousness of depression if needed. If the PHQ-9 is utilized, the completed questionnaire should be archived in the subject's source documents.).
- Numeric Pain Scale rating (IRT) for major joints (bilateral shoulders, hips and knees) and any painful joint imaged at Screening.
- Primary diagnosis and selection of index hip or knee.

**NOTE:** If the subject experiences pain in more than one joint, then the most painful joint should be selected as the index joint. Radiographic eligibility of the selected index joint will need to be confirmed by the Central Reader. In the event the index joint selected at screening does not have a qualifying Kellgren-Lawrence Grade, the sponsor study team may be contacted to discuss the potential for reselection of the index joint and to rescreen the subject providing the subject is not disqualified from study participation for any other reason.

• WOMAC (all subscales via IRT) for index hip or knee.

**NOTE**: Subjects should be thoroughly instructed on completion of WOMAC scales, no coaching or other interpretative assistance should be given to subjects during completion of these questionnaires.

- Comprehensive musculoskeletal/joint related medical history (includes past history of osteoarthritis, osteoporosis, osteopenia, joint pain, injury, trauma, joint surgeries (including arthroscopic procedures), ligament tear or rupture, fractures, gout, joint injuries or other conditions.
- Medication history (record prior 12 month use of medications for osteoarthritis, prior 30 day use for all other medications).
- Weight and Height with BMI calculation, Smoking Status, Alcohol Use/Dependency, Female Hormonal Status (if known or pending laboratory results).
- Vital signs after sitting for at least 5 minutes, (blood pressure, and heart rate).
- Orthostatic blood pressure (supine/standing) measurement.
- General physical examination.
- Musculoskeletal physical examination.
- Neurologic exam/Neuropathy Impairment Score.
- Survey of Autonomic Symptoms (SAS).
- ECG (12-lead).
- X-rays of each knee, hip and shoulder (and any other painful, major joint if appropriate) and collect local radiology report.
- Clinical laboratory tests (blood chemistry, hematology, and urinalysis, serum Hepatitis B, C, and HIV screen, urine toxicology screen, HbA1c), serum pregnancy testing/FSH testing if needed.

**NOTE:** Clinically significant abnormal laboratory tests (except urine toxicology screen) or tests not meeting inclusion/exclusion criteria may be repeated for

verification prior to Baseline. Refer to Section 7.3.3 for specific instructions related to laboratory screening tests.

- Inclusion/exclusion review (pending results of laboratory tests, ECG and X-rays). If a subject qualifies other than pending results they may begin the washout of prohibited pain medications (refer to Section 5.8.1). Subjects who are found to be ineligible subsequent to the receipt of disqualifying laboratory, ECG or X-ray results may be asked to return requested study related materials and will exit the Screening period (Screen Failure).
- Female subjects of child-bearing potential will be instructed on the contraception requirements for this study; the investigator or designee will confirm that female subjects of child-bearing potential have selected 2 highly effective forms of contraception from the list of acceptable methods and instruct the subject in their consistent and correct use. The conversation will be documented in the subject chart.
- Dispense Screening period rescue medication; subjects will be instructed on the permissible amounts of rescue medication during the washout period, during the IPAP and during the treatment period, as well as the need to refrain from rescue medication use at least 24 hours prior to a study visit (refer to Section 5.8.2).
- Subjects in Japan who have not had a trial of acetaminophen (as monotherapy or in combination with tramadol) for their osteoarthritis, will undergo at least 1-week trial of an approved daily dose of acetaminophen after obtaining informed consent because subjects are required to have documentation that acetaminophen has not provided sufficient pain relief. The 1-week trial of acetaminophen should be completed at least two weeks prior to the Baseline/Day 1 visit. If they obtain sufficient response to acetaminophen, as judged by the subject and Investigator, they will then be withdrawn from the study. Those who do not have a sufficient response to acetaminophen will continue with the screening process. Subjects who have not achieved an adequate response to an approved dose of Tramacet® (1-2 tablets four times a day (QID): total daily tramadol 150 mg 300 mg and acetaminophen 1300 mg 2600 mg) can be considered to meet the acetaminophen and tramadol inclusion criterion.
- Dispense Screening period oral NSAID.

**NOTE:** Begining at Screening, subjects should use study-supplied oral investigational product (NSAID during Screening and NSAID or matching placebo post-randomization) through Week 56.

Subjects who were receiving celecoxib, diclofenac or naproxen prior to Screening will receive this same oral NSAID but may need to change dosing regimen to a BID dosing regimen for the duration of the study. Subjects must maintain the BID dosing regimen of celecoxib 100 mg, naproxen 500 mg, or diclofenac ER 75 mg for at least

the final 2 weeks of the Screening period directly prior to the Baseline (Randomization/Day 1) Visit.

Subjects who were receiving aceclofenac, loxoprofen, ibuprofen, meloxicam, nabumetone, sulindac or ketoprofen prior to Screening will be assigned to celecoxib, naproxen or diclofenac. The specific NSAID that subjects will be assigned to (celecoxib, naproxen or diclofenac) will be the choice of the investigator. Subjects will use this NSAID for the remainder of the Screening period and will be stabilized on a dosing regimen of celecoxib 100 mg BID, naproxen 500 mg BID, or diclofenac ER 75 mg BID for at least the final 3 weeks of the Screening period directly prior to the Baseline (Randomization/Day 1) visit.

During NSAID regimen stabilization, all subjects will be expected to maintain a minimum compliance of 70% (average of 5 of 7 days per week).

## 6.1.2. Screening Period Stage 2

Subjects who satisfy inclusion/exclusion criteria (to this point) and for whom radiographic eligibility has been confirmed, will undergo the following additional screening procedures:

- MRIs of each hip and knee (all subjects).
- DXA scans of the hip and lumbar spine.

**NOTE**: DXA scans will only be performed for subjects meeting National Osteoporosis Foundation recommendations for bone mineral density testing (refer to Section 7.3.12).

- Subjects at selected sites will be provided with activity level monitors (accelerometers) and instructions on completion of 7 consecutive days of activity monitoring (refer to Section 7.3.9).
- Subjects will be instructed in the use of the IRT system to record daily/weekly pain ratings, rescue medication use, with specific instructions as when to test the system and when to begin entering data.
- Subjects will maintain the BID dosing regimen of celecoxib 100 mg, naproxen 500 mg, or diclofenac ER 75 mg for at least the final 2 or 3 weeks (average of 5 of 7 days per week; ie, minimum 70% compliance) of the Screening period directly prior to the Baseline (Day 1) visit.

## 6.1.3. Washout Period

The beginning of the Washout Period will preferably be scheduled based on the planned start of the Initial Pain Assessment Period so as to minimize the time spent without analgesic medications prior to Randomization. The Washout Period will include the discontinuation and washout of all prohibited medications for at least 5 half-lives or 48 hours (whichever is greater) prior to the Initial Pain Assessment Period (the 7 days prior to randomization) and will be a minimum of 2 days (Refer to Appendix 3). Subjects experiencing pain during the Washout Period may take acetaminophen as needed up to 3000 mg per day, but must discontinue rescue medication for at least 24 hours prior to the Baseline (Randomization) Visit.

If necessary, the Screening/Washout Period may be adjusted due to individual subject circumstances (eg, stabilization of a concomitant medication), contact study management for guidance. However, the total duration of the Screening period is not to exceed 37 days.

## 6.1.4. Initial Pain Assessment Period (IPAP)

The IPAP will begin approximately 7 days (minimum of 3 days) prior to the Baseline (Day 1) randomization visit, and subjects must complete at least 3 diary entries during the IPAP period, but all diary entries will be used to determine the baseline value for the average pain score in the index joint.

• During this time, subjects will record daily pain scores for their index joint (knee or hip) and rescue medication use via the IRT (refer to Sections 7.1.1 and 7.1.2). Assessment of the non-index joint pain will be performed once during the IPAP.

**NOTE:** Study sites will monitor the IRT reports for compliance with diary recordings and rescue medication use and reschedule those subjects who fail to provide 3 diary days or fail to refrain from rescue medication use 24 hours prior to Baseline.

## 6.2. Double-Blind Treatment Period

The Double-blind Treatment period begins with the Baseline (Day 1) visit and concludes with completion of the Week 56 visit procedures. The Double-blind Treatment period is 56 weeks in duration and consists of 10 clinic visits (Day 1 and Weeks 2, 4, 8, 16, 24, 32, 40, 48 and 56) and 6 telephone contacts (Weeks 12, 20, 28, 36, 44, 52) between site staff and study subjects.

# 6.2.1. Baseline (Day 1) Clinic Visit

# 6.2.1.1. Assessment of Randomization Criteria and Randomization

Subjects must continue to satisfy Inclusion/Exclusion Criteria [general criteria and those specific to the Baseline (Day 1) visit – refer to Section 4.3] to be eligible for Randomization. Full eligibility, including (but not limited to) confirmation of appropriate washout of concomitant medication, compliance with NSAID treatment regimen stabilization, abstinence from acetaminophen in the previous 24 hours, completion of at least 3 diary entries in the past 7 days, required WOMAC Pain and Physical Function subscale and Patient's Global Assessment of Osteoarthritis scores, required MRI and DXA scans (if appropriate) have been obtained and that no adverse events occurred since signing informed consent that would render the subject ineligible for randomization, should be assessed before carrying out randomization in the IRT system.

Subjects will undergo the following assessments prior to randomization:

- Sites performing activity level monitoring (actigraphy) will collect activity level monitors from subjects.
- Inclusion/exclusion review (including results of ECG, laboratory and X-rays obtained at the Screening visits).
- WOMAC (all subscales).
- Patient's Global Assessment of Osteoarthritis.

**NOTE**: Subjects should be thoroughly instructed on completion of Patient's Global Assessment of Osteoarthritis questionnaires, no coaching or other interpretative assistance should be given to subjects during completion of these questionnaires.

- Musculoskeletal physical examination.
- Vital signs after sitting for at least 5 minutes, (blood pressure, and heart rate).
- Orthostatic blood pressure (supine/standing) measurement.
- Review of concomitant medication.
- Rescue medication (acetaminophen/paracetamol) review.
- Baseline NSAID compliance review.
- Instruction/review of subject compliance with daily/weekly assessments and operation of the IRT.
- Confirm with females of child-bearing potential that they understand and are willing to follow the contraceptive requirements.
- Adverse events that occurred after signing the Informed Consent Document (pretreatment adverse events).
- Urine pregnancy test for females of childbearing potential (must be negative).

## 6.2.1.2. Randomization

Subjects satisfying eligibility requirements will be randomized via an IRT system. The randomization number assigned to the subject will be provided by the system. Subjects satisfying eligibility requirements will undergo the following assessments prior to the first dose of investigational product.

## 6.2.1.3. Pre-dosing (Day 1)

Randomized subjects will undergo the following assessments prior to the first dose of investigational product. Some of these may be performed prior to randomization for convenience:

- WPAI:OA.
- EQ-5D-5L.
- Assessment of Health Care Resource Utilization.
- Lower Extremity Activity Scale (LEAS).
- Neurologic exam/Neuropathy Impairment Score.
- Clinical laboratory tests (blood chemistry and hematology).
- Serum samples for 25-hydroxy vitamin D and parathyroid hormone.
- Serum and plasma retention samples.
- Blood sample for anti-tanezumab antibody assessment (refer to Section 7.3.14).
- Blood samples for PK and PD (NGF) analyses (refer to Section 7.5).
- Blood and urine samples for biomarkers (fasting if possible, urine sample should be from 2nd void of the day or after; refer to Section 7.6).
- Blood sample for banked biospecimens (see Section 7.7.1 Markers of Drug Response and Additional Research, Section 7.7.2).
- Dispense rescue medication.
- Dispense oral investigational product (NSAID or matching placebo).
- Females of child-bearing potential to be reminded of contraceptive requirements.

## 6.2.1.4. Dosing (Day 1)

• Subjects will receive a single SC injection of blinded investigational product according to the treatment assigned by the IRT system (refer to Section 5).

The administration of investigational product must be performed by trained medical staff and where facilities to handle allergic reactions are available (eg, diphenhydramine hydrochloride for injection, epinephrine 1:1000 for management of acute or severe reactions such as anaphylaxis). Should a subject experience symptoms typical of an allergic reaction (eg, shortness of breath, anaphylaxis, urticaria, angioedema), then investigational product

administration should be discontinued immediately and permanently. Subjects will receive appropriate treatment such as corticosteroids, antihistamine, or acetaminophen at the discretion of the Investigator. No other dosage modifications are allowed.

• A morning dose of oral investigational product (NSAID or matching placebo) will not be administered on Study Day 1. The evening dose of oral investigational product on Study Day 1 and all subsequent dosing of oral investigational product will be performed by subjects at home.

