# 7.4. Triggered Requirements and Subject-Level Stopping Rules

The following rules will apply to individual subjects at the time of the second and subsequent injections of SC investigational product.

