# 7.4.1. Dysesthesia/Allodynia

Transient, resolved dysesthesia/allodynia: Administer SC investigational product as planned as long as the condition has resolved before the next scheduled dose of SC investigational product.

Unresolved dysesthesia/allodynia: Withhold the SC investigational product for a maximum of 14 days beyond the planned dosing day to allow for resolution of the adverse event. If the dysesthesia/allodynia has not resolved within the 14-day period after the scheduled dosing date, the subject will not receive any additional doses of investigational product and will enter the Early Termination Follow-up period (refer to Section 6.4).

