# 7.4.2. Hypersensitivity or Injection Site Reactions

If a severe hypersensitivity reaction or severe injection reaction occurs following any administration of SC investigational product, the investigational product should be discontinued immediately and no further administrations of SC investigational product will

be allowed. Subjects experiencing these types of reactions will enter the Early Termination Follow-up period (refer to Section 6.4).

Severe hypersensitivity reactions are defined as those causing anaphylaxis. Severe injection site reactions are defined as those in which ulceration or severe necrosis occurs.

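### Sections 6.2.1.4 and 7.4.2 of the protocol set different allergic-reaction thresholds for stopping SC dosing, and read narrowly they leave no stop rule short of anaphylaxis after the Week 8 to 48 doses

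*Protocol*

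**What the plan says.** Two places in the protocol govern what happens after an allergic reaction to the SC product.

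- **Section 6.2.1.4 (Dosing, Day 1).** The trigger is broad: "Should a subject experience symptoms typical of an allergic reaction (eg, shortness of breath, anaphylaxis, urticaria, angioedema" and so on. The consequence is that product "administration should be discontinued immediately and permanently". After a sentence on treating the reaction, the paragraph ends: "No other dosage modifications are allowed".
- **Section 7.4.2 (Hypersensitivity or Injection Site Reactions).** The trigger is narrower: "If a severe hypersensitivity reaction or severe injection reaction occurs following any administration of SC investigational product", SC dosing ends. The term is then defined: "Severe hypersensitivity reactions are defined as those causing anaphylaxis". Injection site ulceration or severe necrosis is a separate trigger. On follow-up it says: "Subjects experiencing these types of reactions will enter the Early Termination" Follow-up period.

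The parent Section 7.4 opens with its scope: "The following rules will apply to individual subjects at the time of the second and subsequent injections of SC investigational product".

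Section 6.2.1.4 refers the reader only to Section 5, and 7.4.2 only to Section 6.4. The SC dosing subsections for Weeks 8, 16, 24, 32, 40 and 48 carry no allergic-reaction stop wording. They refer to Section 5, where 5.5.1 requires facilities able to manage allergic reactions but gives no stopping rule. The SAP does not address the point.

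**The concern.** This is a subject-level safety rule for an antibody given by up to seven injections. A subject with angioedema or generalised urticaria that falls short of anaphylaxis meets the trigger in one section and not in the other. The broader rule sits under a Day 1 heading. The narrower one sits in the section a site would naturally open to decide on a later dose.

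The neighbouring rule shows what is missing. Section 7.4.1 on dysesthesia and allodynia covers both sides of its threshold: it says when to go on ("Administer SC investigational product as planned as long as the condition has resolved before the next scheduled dose") and when to stop. Section 7.4.2 covers only the severe side and says nothing about a milder allergic reaction.

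What is at stake is whether subjects with the same reaction to a later dose are handled the same way at different sites, and whether a subject with a non-anaphylactic reaction is protected by a rule or only by judgement.

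**Working it through.** There is no figure to reproduce. The check applies the two rules to each type of reaction at each dose, and then looks for text elsewhere that reconciles them.

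**Inputs.** Trigger and action from 6.2.1.4; trigger, definition and action from 7.4.2; scope from 7.4; SC doses at Baseline and Weeks 8, 16, 24, 32, 40 and 48, which is 1 + 6 = 7.

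| Reaction | 6.2.1.4 | 7.4.2 | Result |
|---|---|---|---|
| Anaphylaxis, Day 1 | Stop | Stop | Stop |
| Anaphylaxis, doses 2 to 7 | Stop if read as general | Stop | Stop on either reading |
| Allergic symptoms without anaphylaxis, Day 1 | Stop | Silent | Stop |
| The same, doses 2 to 7, 6.2.1.4 read as general | Stop | Silent | Stop |
| The same, doses 2 to 7, 6.2.1.4 read as Day 1 only | Does not apply | Silent | No mandatory stop |

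**Day 1.** Day 1 is a single injection, so a permanent stop ordered there can only concern later doses. Section 7.4.2 adds nothing for a non-anaphylactic reaction but takes nothing away. The Week 8 dose is barred on any reading.

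**Doses 2 to 7.** The outcome turns on whether 6.2.1.4 is general or confined to its heading.

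- If general, every case stops, and the anaphylaxis threshold in 7.4.2 has no work to do.
- If Day 1 only, 7.4.2 is the only stated rule, and it does not reach urticaria, angioedema or breathlessness without anaphylaxis.

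**Search for a reconciling rule.**

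- Section 5.5.1 and the later dosing subsections contain none.
- The post-dosing text at all seven dosing visits tells subjects to seek care for the same four symptoms, described there as acute or severe hypersensitivity. That is a wider idea of severity than the 7.4.2 definition, but it is not a stop instruction.
- Section 9.6.1.1 names anaphylactic events only, and it is a protocol-level rule.
- Section 6.4 lets the investigator or sponsor withdraw a subject for safety at any time. That is discretion, not a rule.

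**The case against.** The strongest reply is that no contradiction exists. Section 7.4.2 lists when dosing must stop and nowhere allows a further dose after a milder reaction, so a site complies with both sections by following 6.2.1.4. That is correct.

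The reply goes on that the general reading of 6.2.1.4 is the more natural one. Its paragraph sets staffing and facility requirements that 5.5.1 repeats for SC dosing at large, and a ban on other dosage changes means little for one injection. On that view the later dosing subsections are short because the rule has already been given, and 7.4.2 is merely redundant for hypersensitivity. This has force, but the text does not settle it: the paragraph stands under a Day 1 heading, no later section points back to it, and the definition in 7.4.2 would be odd if it were meant to have no effect.

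A reader might infer that the protocol licenses re-dosing after non-anaphylactic angioedema, or that two sites could act in opposite ways with equal textual support. The documents do not support that. After a Day 1 reaction, re-dosing would breach 6.2.1.4. After a later dose, a site that re-doses could point only to silence in 7.4.2, not to permission.

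Nor does counting symptoms or dosing subsections measure the problem. The symptom list is only a set of examples with clinical overlap, and the counts say nothing about how many subjects are affected.

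**Conclusion.** The thresholds differ, neither section refers to the other, and no other text reconciles them. The practical consequence is confined to allergic reactions short of anaphylaxis after doses 2 to 7, at a site that takes 6.2.1.4 to cover Day 1 only. There the subject's protection is discretionary withdrawal under Section 6.4.

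The number of subjects cannot be estimated. Neither document gives a rate for these reactions, and Table 2 of the protocol lists no hypersensitivity, urticaria, angioedema or anaphylaxis among the expected reactions, so few subjects may be involved. This is a clarity fault in a safety rule. It has no claimed effect on alpha or power. It is still worth correcting, because the rule decides whether an individual is re-exposed and the correction is wording only.

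The conclusion rests on one assumption: that a site could reasonably read 6.2.1.4 as limited by its heading.

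**What to change.** Amend 7.4.2 so that typical allergic symptoms, with the four examples already given in 6.2.1.4, permanently stop SC dosing when the investigator considers them related to any SC injection, Day 1 included, with entry to Early Termination Follow-up. Keep the injection site criteria as they are. Cross-reference 6.2.1.4 and 7.4.2 so that one wording governs every dose.

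The relatedness condition is needed. Without it, urticaria from an unrelated cause at any time in an 8-week dosing interval would end treatment.

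The broader trigger is the protocol's own. It also fits exclusion criterion 27, which bars a history of allergic as well as anaphylactic reaction to a monoclonal antibody, although that criterion concerns entry and does not set an on-study threshold.

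**Cost.** An amendment or clarification, with no new procedure. A few more subjects with milder reactions would stop SC dosing. Any who stop before Week 16 for an adverse event and have missing Week 16 data would be imputed around their baseline value (Protocol 9.2.1, SAP Section 7). That exposure is limited. Day 1 reactions already stop, and the Week 16 assessments precede the Week 16 dose, so only the Week 8 dose can add such stops. For those subjects, Early Termination Visit 1 falls at about Week 8 + 8 = Week 16 and collects the co-primary measures, which SAP Section 8 counts as on-treatment.
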